
8.4.3 Other endpoints

Patient reporting of CTCAE symptoms

The PRO-CTCAE questionnaire will be used to derive patient reporting of CTCAE symptoms: nausea, vomiting, diarrhea, decreased appetite, fatigue, and dizziness.

Safety variables

Safety and tolerability will be assessed in terms of AEs, deaths, laboratory data, vital signs including BP and ECGs. Any AE occurring before the start of IP will not be included in the summary tables of AEs.

Any AE occurring within 30 days of discontinuation of IPs (ie, the last dose of cediranib + olaparib) or the last dose of the last IP to be discontinued, in the rare case where discontinuation dates are different will be included in the AE summaries.

Blood pressure data collected electronically (see Section 5.2.4.1) will not be reported in the CSR. Patient profiles and BP data over time for patients may be evaluated in an exploratory analysis at a later time.

8.5 Methods for statistical analyses

Descriptive statistics will be used for all variables, as appropriate. Continuous variables will be summarized by the number of observations, mean, standard deviation, median, minimum, and maximum. Categorical variables will be summarized by frequency counts and percentages for each category. Unless otherwise stated, percentages will be calculated out of the FAS.

Baseline will be the last assessment of the variable under consideration prior to the intake of the first dose of IP.

8.5.1 Analysis of the primary variable ORR

The primary analysis will be based on ICR assessments of tumor response. Only patients with a confirmed CR or PR, by ICR, at least 4 weeks after the initial response will be counted as responders.

The number of responders (confirmed CR or PR) will be modelled using a binomial distribution with a neutral Beta (1/3,1/3) prior distribution on the rate.

The mean and median of the posterior distribution of ORR will be presented, along with the standard deviation and a 95% credible interval around the mean (based on the highest posterior density [Lee, 1997]). The observed ORR by ICR will also be presented with 95% exact (Clopper Pearson) CIs.

The posterior probabilities of the ORR being larger than 15%, 20% and 24% will be also computed. To further characterize the RR, the posterior probability of showing low (<15%), moderate ($\geq 15\%$ - <20%), high ($\geq 20\%$ - <24%) or substantial ($\geq 24\%$) efficacy will be presented.

Summaries of the number of patients with best response in each of the follow categories will be presented: CR, PR, SD, PD and NE. For the interim analysis, the CR (PR) category will be split into confirmed CR (PR) and unconfirmed CR (PR).

At the time of primary analysis, ORR and exact 95% CI (Clopper Pearson) will be also be presented for the following:

- ORR by investigator assessment
- ORR for both confirmed and unconfirmed responses based on ICR assessment
- ORR based on ICR assessment in the subgroup of patients carrying a somatic deleterious or suspected deleterious variant in either of the *BRCA* genes (*BRCA1* or *BRCA2*) or in HRR-associated genes identified with current and potential future tumor based *BRCA* or HRR gene mutation assays (ICR and Investigator assessment)

The concordance between ORR (confirmed responses) as assessed by ICR and by Investigator will be presented.

8.5.2 Analysis of the secondary variable(s)

Disease Control Rate (DCR)

DCR is defined as confirmed CR, PR or SD for at least 6 months. DCR based on ICR in the evaluable for response analysis set will be presented together with 95% exact (Clopper Pearson) CIs. DCR will be presented based on the Investigator assessment as a sensitivity analysis.

Duration of response (DoR)

DoR in responding patients will be summarized and the number (%) of responding patients with a DoR >3, >6, >9 and >12 months will be presented. A Kaplan Meier plot and median DoR with 95% CI (calculated from the Kaplan-Meier plot) will be presented. DoR will be presented based on the ICR, and (as a sensitivity analysis) based on the Investigator assessment.

Progression free survival (PFS)

PFS will be displayed using a Kaplan Meier plot. The number of events, the type of event (RECIST 1.1 progression or death), median time to event (calculated from the Kaplan-Meier plot), and the proportion of patients without an event at 3, 6, 12 and 18 months will be summarized.

Overall survival (OS)

OS will be displayed using a Kaplan-Meier plot. The number of events, median time to event (calculated from the Kaplan-Meier plot), and the proportion of patients without an event at 3, 6, 12 and 18 months will be summarized.

Subsequent anticancer treatment

Subsequent anticancer treatment will be summarized descriptively at the primary analysis.

Time to discontinuation of study treatment or death (TDT)

TDT will be displayed using a Kaplan-Meier plot. The number of events, median time to event (calculated from the Kaplan-Meier plot), and the proportion of patients without an event at 3, 6, 12 and 18 months will be summarized.

HRQoL Assessments

HrQoL data will be presented using summaries and descriptive statistics, and will be detailed in the SAP.

Safety Assessments

Safety and tolerability data will be presented using summaries and descriptive statistics, and will be detailed in the SAP.

8.5.3 Subgroup analysis (if applicable)

The analyses of ORR, DCR, DoR, PFS and OS will be repeated for patients in and not in the following two subgroups:

- patients carrying a somatic deleterious or suspected deleterious variants in either of the *BRCA* genes (*BRCA1* or *BRCA2*) identified with current and potential future tumor based *BRCA* mutation assays
- patients identified as having a deleterious or suspected deleterious variants in HRR-associated genes identified with current and potential future HRR gene mutation assays.

Other subgroups may be analyzed, as detailed in the SAP.

8.5.4 Interim analysis

An interim futility analysis will take place after 20 evaluable (by Investigator assessment) patients have received IPs and have been followed for at least 4 months. The study may be stopped for futility if there are less than 4 responders (confirmed and/or unconfirmed responses) out of the first 20 patients in which case the predictive probability of observing 30 responders or more at the end of trial is $\leq 4.6\%$. Computation of posterior and predictive probabilities will use a neutral prior ie, beta (1/3, 1/3) distribution (Kerman 2011), for the ORR. The predictive probability of observing a given number of responses at the end of the trial given the observed responses at the interim analysis is computed using a beta binomial distribution.

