8.2 Sample size estimate

The study originally planned to recruit 100 patients over approximately 12 months. The primary analysis scheduled at 8 months after the last patient received her first dose of IP (approximately 20 months after study start), allows all patients to have at least 4 RECIST follow-up assessments.

An interim futility analysis of ORR (confirmed and/or unconfirmed CRs and PRs based on investigator assessment) will take place after 20 evaluable patients (ie, with measurable disease (by Investigator assessment) have received at least 1 dose of IP and have been followed for at least 4 months. If less than 4 of the 20 have responded the study may be stopped for futility. If 4 or more patients have responded the study will continue to the primary analysis.

The study design was formulated within a Bayesian framework (Fisch et al 2015) based on dual criteria to show improvement over the expected response rate under current standard treatments (20% RR targeted as an improvement over <15% RR based on chemotherapy, Davis et al 2014) and to have a RR of a relevant size (approximately 30%, similar to the RR seen for bevacizumab plus chemotherapy in the AURELIA trial, Pujade-Lauraine et al 2014) defined as follows:

1. to have high confidence (>90%) that the true ORR is at least 20% or probability ($ORR \geq 20\%$) >0.9 and
2. an observed rate of 30/100 is seen at the primary analysis.

The futility rule above (stop if number of responses is <4), was chosen so that the trial may stop if there is a low chance (<10% predictive probability) of 30 or more responses being observed at the primary analysis. Computation of posterior and predictive probabilities used a neutral prior ie, beta (1/3, 1/3) distribution (Kerman 2011), for the ORR. The predictive probability of observing a given number of responses at the end of the trial given the observed responses at the interim analysis is computed using a beta binomial distribution.

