With 30 responders out of 100 at the primary analysis we would be >99% confident that the ORR is greater or equal to 20% and 94.6% confident that the ORR is $\geq 23\%$. It is noted that the interim analysis is based on unconfirmed, investigator assessed RECIST data, whereas the primary analysis will be based on ICR assessed data with responses confirmed at least 4 weeks after the initial response. Data from the OCEANS study indicated an approximate 1.5% reduction in response by ICR compared with investigator response (Aghajanian et al 2014). If only 26 patients out of 100 were to meet the latter definition of response at the primary analysis there would still be >90% confidence that the true rate was greater than or equal to 20%.

Assuming median PFS of 6 months, 73% PFS events are expected at the primary analysis at 8 months after the last patient receives her first dose of IP. The original analysis for OS at 12 months after last patient receives her first dose of IP would expect 59% deaths.

The study now plans to recruit approximately 60 patients and analysis of OS, originally planned at 12 months after the last patient received her first dose of IP, will now occur at 8 months after the last patient received her first dose of IP. Based on the revised duration of recruitment and assuming a median PFS of 6 months as originally planned and a median of 12 months for OS, 80% PFS events and 57% OS events are expected to occur at the time of the analysis.

Table 18 presents the 95% CIs for some possible response rates which give an indication of the precision of the response rate that might be seen.

Table 18 Response rates and associated 95% CIs for a sample of 60

Response (n)	Response (%)	95% CI
5	8.3%	(1.3%, 15.3%)
10	16.7%	(7.2%, 26.1%)
15	25.0%	(14.0%, 36.0%)

CI confidence interval

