1.3 Number of patients

The study originally planned to recruit 100 patients over approximately 12 months. Due to slower than projected recruitment, the study now plans to recruit approximately 60 patients. The primary analysis scheduled at 8 months after the last patient received her first dose of IP (approximately 20 months after study start), allows all patients to have at least 4 RECIST follow-up assessments.

An interim futility analysis of ORR (confirmed and/or unconfirmed CRs and PRs based on investigator assessment) will take place after 20 patients have received at least 1 dose of IP and have had opportunity to be observed for at least 4 months. If less than 4 of the 20 have responded the study may be stopped for futility. If 4 or more patients have responded the study will continue to the final analysis.

The study design was formulated within a Bayesian framework (Fisch et al 2015) based on dual criteria to show improvement over the expected response rate (RR) under current standard treatments (20% RR targeted as an improvement over <15% RR based on chemotherapy, Davis et al 2014) and to have a RR of a relevant size (approximately 30%, similar to the RR seen for bevacizumab plus chemotherapy in the AURELIA trial, Pujade-Lauraine et al 2014) defined as follows:

1. to have high confidence (>90%) that the true ORR is at least 20% or probability ($ORR \geq 20\%$) >0.9 and
2. an observed rate of 30/100 is seen at the final analysis.

The futility rule above (stop if number of responses is <4), was chosen so that the trial may stop if there is a low chance (<10% predictive probability) of 30 or more responses being observed at the final analysis. Computation of posterior and predictive probabilities used a neutral prior i.e. beta (1/3, 1/3) distribution (Kerman 2011), for the ORR. The predictive probability of observing a given number of responses at the end of the trial given the observed responses at the interim analysis is computed using a beta binomial distribution.

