With 30 responders out of 100 at the final analysis we would be >99% confident that the ORR is greater or equal to 20% and 94.6% confident that the ORR is $\geq 23\%$. It is noted that the interim analysis is based on unconfirmed, investigator assessed RECIST data, whereas the final analysis will be based on ICR assessed data with responses confirmed at least 4 weeks after the initial response. Data from the OCEANS study indicated an approximate 1.5% reduction in response by ICR compared with investigator response (Aghajanian et al 2014). If only 26 patients out of 100 were to meet the latter definition of response at the final analysis there would still be >90% confidence that the true rate was greater than or equal to 20%.

Assuming median PFS of 6 months, 73% PFS events are expected at the primary analysis at 8 months after the last patient receives her first dose of IP.

The original analysis for OS at 12 months after last patient receives her first dose of IP would expect 59% deaths.

The study now plans to recruit approximately 60 patients and analysis of OS, originally planned at 12 months after the last patient received her first dose of IP, will now occur at 8 months after the last patient received her first dose of IP. Based on the revised duration of recruitment and assuming a median PFS of 6 months as originally planned and a median of 12 months for OS, 80% PFS events and 57% OS events are expected to occur at the time of the analysis.

Table 1 Response Rates and associated 95% CIs for a sample size of 60

Response (n)	Response (%)	95% CIs
5	8.3%	(1.3%, 15.3%)
10	16.7%	(7.2%, 26.1%)
15	25.0%	(14.0%, 36.0%)

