5. INTERIM ANALYSES

An interim futility analysis will take place after 20 evaluable (by Investigator assessment) patients are recruited and have had opportunity to be observed for at least 4 months, and datasets required are clean. The primary endpoint of the interim futility analysis will be the number of responders using the investigators assessment of RECIST 1.1. The study may be stopped for futility if there are less than 4 responders out of the first 20 patients in which case the predictive probability of observing 30 responders or more at the end of trial is $\leq 4.6\%$.

A summary of the ORR will be presented for the interim population, along with a two-way table illustrating the concordance of the baseline scans between local assessment and ICR with respect to whether there was measurable disease at baseline.

For the purposes of the interim analyses a responder is defined as a patient with measurable disease at baseline, with at least one confirmed or unconfirmed visit response of CR or PR.

No formal outputs beyond assessment of ORR, and concordance of the population with ICR, are planned to be generated at the interim analysis.

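### After the cut to about 60 patients, criterion 2 (30/100), its assurance figures and the 4.6% futility probability are still the 100-patient values, and no figures for 60 replace them

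*Protocol*

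**What the plan says.** **Sample size.** Protocol 8.2 gives 100 as the original plan and then says "The study now plans to recruit approximately 60 patients and analysis of OS" moves to 8 months after the last first dose. SAP 1.3 has the same change, and the SAP amendment history records that the sample size was updated.

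**Criteria.** Protocol 8.2 sets two: more than 90% posterior confidence that the ORR is at least 20%, and "an observed rate of 30/100 is seen at the primary analysis". SAP 1.3 has "an observed rate of 30/100 is seen at the final analysis". The motivation given for the second is a relevant response rate of about 30%.

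**Assurance.** Both sections say that 30 responders out of 100 give more than 99% confidence in an ORR of at least 20%, and 94.6% in at least 23%. The fallback reads "If only 26 patients out of 100 were to meet the latter definition of response at the primary analysis there would still be" more than 90% confidence in at least 20% (Protocol 8.2; SAP 1.3 has the same sentence for the final analysis).

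**Futility.** The rule of stopping below 4 of 20 was chosen so that the trial may stop when there is under a 10% predictive chance of "30 or more responses being observed at the primary analysis" (Protocol 8.2). Protocol 8.5.4 says of a result below 4 in 20, "in which case the predictive probability of observing 30 responders or more at the end of trial is" no more than 4.6%. SAP 5 reads "the predictive probability of observing 30 responders or more at the end of trial is" at most 4.6%. Neither of these two sentences gives a total sample size.

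**What was added for 60.** Protocol Table 18 and SAP Table 1 give confidence intervals for 5, 10 and 15 responders. The expected event percentages for PFS and OS were also revised (80% and 57%).

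**The concern.** The two criteria are the only benchmark in the plan for a worthwhile response rate, and the 4.6% is the printed justification for the futility boundary. Both belong to a trial of 100. The PFS and OS event percentages were recalculated for the smaller trial in the same sections; the Bayesian figures were not. Part of Protocol 8.2 can be read as history, because it speaks of what was originally planned and how the design was formulated. The futility sentence in Protocol 8.5.4 and SAP 5 carries no such label and refers to the end of the trial, which is now about 60 patients.

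At stake is whether the stated design properties describe the trial being run. As the text stands, the author of the study report must either rescale criterion 2 once the data are known or quote assurance that belongs to a different sample size.

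**Working it through.** **Inputs.** Prior Beta(1/3,1/3), beta-binomial prediction, 20 patients at the interim, boundary below 4 responders, standard of under 10% predictive probability, criterion 1 of P(ORR ≥ 20%) > 0.9, and criterion 2 of 30/100 (Protocol 8.2 and 8.5.4; SAP 1.3 and 5). Current size: about 60.

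**Formulas.** For x responders in n patients, the posterior is Beta(1/3 + x, 1/3 + n − x), and assurance is its upper tail above 20% or 23%. For a final target of R out of N, given x of 20, the predictive probability is P(Y ≥ R − x), where Y is beta-binomial over N − 20 further patients with parameters 1/3 + x and 1/3 + 20 − x.

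**Step 1: reproduce the printed figures at N = 100.**
- 30/100, posterior Beta(30.33, 70.33): 99.1% for ORR ≥ 20% (printed: more than 99%) and 94.7% for ORR ≥ 23% (printed: 94.6%).
- 26/100: 92.7% for ORR ≥ 20% (printed: more than 90%). 25/100 gives 88.8%, so 26 is the smallest count that qualifies.
- At least 30/100 from 3/20 needs 27 or more in 80 further patients: 4.57% (printed: at most 4.6%). From 4/20: 13.9%.

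Beta(1,1) and Beta(1/2,1/2) priors give 6.6% and 5.1% from 3/20, so the printed 4.6% is the stated prior with a total of 100.

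**Step 2: the same quantities at N = 60.** Scaling criterion 2 to a 30% rate gives 0.30 × 60 = 18. This scaling is an assumption, taken from the stated rate of about 30%.

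| Responders/60 | Rate | P(ORR ≥ 20%) | P(ORR ≥ 23%) |
|---|---|---|---|
| 15 | 25.0% | 82.7% | 64.3% |
| 16 | 26.7% | 89.4% | 74.7% |
| 17 | 28.3% | 93.9% | 83.1% |
| 18 | 30.0% | 96.7% | 89.5% |

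A 26% rate would be 0.26 × 60 = 15.6 responders. Neither 15 nor 16 passes 90%; 17 does.

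At least 18/60 from 3/20 needs 15 or more in 40 further patients: 3.6%. From 4/20 it needs 14 or more: 12.6%.

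**Step 3: allow for a smaller primary analysis set.** The primary analysis uses patients with measurable disease by central review (the EFR set), and the documents give no expected size for it. I assume n = 50 to 60 and round the 30% target up to a whole patient.

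| n | 30% target | Minimum for P(ORR ≥ 20%) > 0.9 | Predictive from 3/20 | Predictive from 4/20 |
|---|---|---|---|---|
| 50 | 15 | 14 | 3.1% | 11.8% |
| 51 | 16 | 15 | 2.2% | 9.0% |
| 52 | 16 | 15 | 2.7% | 10.3% |
| 53 | 16 | 15 | 3.2% | 11.7% |
| 54 | 17 | 15 | 2.3% | 9.1% |
| 55 | 17 | 15 | 2.7% | 10.3% |
| 56 | 17 | 16 | 3.2% | 11.5% |
| 57 | 18 | 16 | 2.4% | 9.1% |
| 58 | 18 | 16 | 2.8% | 10.2% |
| 59 | 18 | 16 | 3.2% | 11.4% |
| 60 | 18 | 17 | 3.6% | 12.6% |

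From 3/20 the probability is below 10% throughout. From 4/20 it dips just under 10% at n = 51, 54 and 57, because the target is rounded up there.

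**The case against.** The strongest reply is that nothing operational depends on these figures. Protocol 8.5.1 and SAP 4.2.7.1 attach no decision to either criterion. The posterior probability that the ORR exceeds 20% will be reported at the actual sample size, so criterion 1 can be read off directly. The statement of at most 4.6% also remains true as an upper bound. All of this stands, and it confines the point to documentation.

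A second reply is that the interim may have been run before the cut. The estimated timetable (first patient Q1 2017, last patient completed by Q3 2019, cut-off 8 months after the last first dose) puts the last first dose at about January 2019, the month of protocol version 5. If so, 4.6% was the correct figure for the decision it supported. This is an inference from estimated dates: both documents still describe the interim in the future tense and do not say that it was done. It affects how values for 60 should be labelled, but does not supply the missing ones.

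Two stronger readings are tempting. A reader might take the undenominated target as 30 of 60, a 50% response rate, and conclude that the futility rule contradicts its own rationale. Protocol 8.2 and SAP 1.3 rule this out, because they pair 30 with 100 both in criterion 2 and in the assurance statement. A reader might also say that the printed assurance is inflated. It is not: the 99% and 94.6% are attached to 30 out of 100 and remain true there. They are out of date.

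Table 18 and SAP Table 1 are also not at fault for stopping at 25%. They are offered as an indication of precision.

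**Conclusion.** The point holds as a failure to update. The printed Bayesian figures are correct for 100 patients and do not describe a trial of about 60. Neither document gives a criterion 2, an assurance or a predictive probability for 60, and neither withdraws the dual criteria.

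The size is moderate. At a 30% observed rate, assurance falls from 99.1% to 96.7% (ORR ≥ 20%) and from 94.7% to 89.5% (ORR ≥ 23%). The fallback weakens more: 26% was enough at 100, but 28.3% (17/60) is needed at 60. The boundary of fewer than 4 in 20 survives on the rate reading, since the predictive probability from 3/20 is 2.2% to 3.6% for n = 50 to 60. No planned estimate, boundary or analysis changes.

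This rests on criterion 2 scaling as a 30% rate, on the assumed EFR range, on all 20 interim patients being in the final EFR set, and on one response definition at both looks. The last is a simplification: the interim counts unconfirmed responses by investigator assessment, whereas the primary analysis counts confirmed responses by central review.

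**What to change.** 1. In Protocol 8.2 and SAP 1.3, label the 30/100 and 26/100 figures as the original 100-patient design. In Protocol 8.5.4 and SAP 5, label the 4.6% in the same way and add the denominator of 100.
2. State whether criterion 2 still applies. If it does, express it as an observed confirmed ORR by central review of at least 30% of the actual EFR denominator (18 if n = 60). Keeping it is the sponsor's choice.
3. Give current-size assurance: 18/60 yields 96.7% for ORR ≥ 20% and 89.5% for ORR ≥ 23%. Replace the 26/100 fallback with the minimum count for P(ORR ≥ 20%) > 0.9 by EFR size: 14 at 50; 15 at 51 to 55; 16 at 56 to 59; 17 at 60.
4. Give the predictive probability of a 30% final rate: at 60, 3.6% from 3/20 and 12.6% from 4/20; over the assumed range of 50 to 60, 2.2% to 3.6% and 9.0% to 12.6%, noting the values just under 10% at 51, 54 and 57. If the interim was run under the 100-patient plan, say so and mark these values as retrospective.
5. Keep the boundary of fewer than 4 in 20. An 18/60 row in Protocol Table 18 and SAP Table 1 would help but is optional.

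The cost is protocol and SAP wording, and a stated assurance slightly less favourable than the one now printed. No extra patients are needed.
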